2.1. Multiplicity Adjustment

A prespecified graphical multiple testing approach (Bretz et al. 2009, 2011) will be implemented to control the overall type I error rate at a 2-sided alpha of 0.05 for superiority tests of the hypotheses for the co-primary and key secondary endpoints. Multiple testing adjusted p-values using “Algorithm 2” described by Bretz et al. (2009) will be calculated, and any hypothesis tests with a multiple testing adjusted p-value of less than 0.05 will be considered statistically significant. This graphical approach is a closed testing procedure; hence, it strongly controls the family-wise error rate across all endpoints (Alosh et al. 2014). Each hypothesis is represented as a node in a graph. Directed arrows between the nodes with associated weights represent how alpha is passed from its initial allocation to other nodes.

The following is a list of co-primary and key secondary endpoints to be tested.

Co-Primary endpoints:

[figure not shown]
- [EASI-75 W16] Percentage of participants achieving EASI-75 ($\geq 75\%$ reduction from Baseline in EASI score) at Week 16 in lebrikizumab 250 mg Q2W versus placebo or lebrikizumab 250 mg Q4W versus placebo.
- [IGA0/1 W16] Percentage of participants with IGA score of 0 or 1 and a reduction ≥ 2 points from Baseline to Week 16 in lebrikizumab 250 mg Q2W versus placebo or lebrikizumab 250 mg Q4W versus placebo.

Key secondary endpoints:

- [EASI PCFB W16] Percentage change in EASI score from Baseline to Week 16 in lebrikizumab 250 mg Q2W versus placebo.
- [EASI-90 W16] Percentage of participants achieving EASI-90 ($\geq 90\%$ reduction from Baseline in EASI score) at Week 16 in lebrikizumab 250 mg Q2W versus placebo.

- [Itch NRS-4 W16] Percentage of participants with Itch NRS of ≥ 4 -point at Baseline who achieve a ≥ 4 -point reduction from Baseline to Week 16 in lebrikizumab 250 mg Q2W versus placebo.

The figure below describes the graphical testing scheme.

[figure not shown]
3. Analysis Sets

The following analysis populations are defined:

Population	Description
All Entered Participants	All participants who signed informed consent/assent. Participant flow will be summarized.
Intent-to-Treat (ITT)	All randomized participants, even if the participant does not take the assigned treatment, does not receive the correct treatment, or otherwise does not follow the protocol. Participants will be analyzed according to the treatment group to which they were assigned. Unless otherwise specified, efficacy and health outcome analyses for the Induction Period will be conducted on this population.
Safety Population	All randomized participants who received at least 1 dose of study intervention during the Induction Period. Safety analyses for the Induction Period will be conducted on this population.
Per-Protocol Set (PPS)	All ITT participants who do not have a subset of important protocol deviations that impact the primary efficacy endpoint. Important protocol deviations are defined in a separate document referred to as "The KGAL Trial Issues Management Plan." Primary efficacy analysis for IGA score of 0 or 1 and EASI-75 will be repeated using the PPS.
Maintenance Primary Population (MPP)	All participants who were randomized to lebrikizumab 250 mg Q2W or lebrikizumab 250 mg Q4W at baseline visit (Visit 2, Week 0) and met the response criteria (that is, participants who achieved an IGA score of 0 or 1 and/or EASI-75 at Week 16) and received at least 1 dose of study intervention during the Maintenance Period. Participants will be analyzed according to the treatment to which they were assigned. Only information prior to entering the Escape Arm will be presented. Efficacy, health outcome, and safety analyses for the Maintenance Period will be conducted primarily on the MPP.
Maintenance Secondary Population (MSP)	Participants who were randomized to placebo at baseline visit (Visit 2, Week 0) and continued placebo (that is, participants who achieved an IGA score of 0 or 1 and/or EASI-75 at Week 16) and received at least 1 dose of study intervention during the Maintenance Period. Only information prior to entering the Escape Arm will be presented. Selective efficacy analyses for the Maintenance Period will be conducted on the MSP.

Maintenance W16 Escape Population	Participants who moved to the Escape Arm at Week 16 (either due to not meeting IGA and EASI criteria, or used rescue therapy during the Induction Period), and received at least one dose of study intervention during the Maintenance Period. Selective efficacy analyses for the Maintenance Period will be conducted on the Maintenance W16 Escape Population.
Maintenance W20-64 Escape Population	Participants in MPP or MSP who escaped to lebrikizumab 250 mg Q2W due to EASI-50 non-response at Weeks 20, 24, 28, 32, 36, 40, 44, 48, 52, 56, 60 or 64. Selective efficacy analyses for the Maintenance Period will be conducted on the Maintenance W20-64 Escape Population to assess whether these participants re-gain EASI-50 response or achieve a higher level of response (for example, EASI-75) following re-treatment.
All Maintenance Population	Participants who entered the Maintenance Period and received at least one dose of study intervention during the Maintenance Period.
All Lebrikizumab Safety Population	All randomized participants who received at least 1 dose of lebrikizumab treatment during the Combined Induction and Maintenance Periods including participants who were randomized to placebo at baseline visit (Visit 2, Week 0) and moved to the Escape Arm at Week 16 or later visits in the Maintenance Period. Safety analyses for the Combined Induction and Maintenance Periods will be conducted on the All lebrikizumab Safety Population. Selective safety analyses for the Combined Induction and Maintenance Periods plus the Follow-Up Period will be conducted on the All Lebrikizumab Safety Population.
Pharmacokinetic Analysis	All participants who received at least 1 dose of lebrikizumab and have at least 1 evaluable PK sample.

Abbreviations: EASI-75 = $\geq 75\%$ reduction from baseline in Eczema Area and Severity Index IGA = Investigator's Global Assessment; Q2W = every 2 weeks; Q4W = every 4 weeks; W = Week.

Treatment Groups and Comparisons for Each Study Period and Analysis Population

Study Period	Analysis Population	Treatment Groups	Abbreviation	Inferential Comparisons When Applicable
Induction Period	ITT; Safety; PPS	Placebo; Lebrikizumab 250 mg Q4W; Lebrikizumab 250 mg Q2W; Total	PBO; LEB250Q4W; LEB250Q2W; Total	LEB250Q4W vs PBO; LEB250Q2W vs PBO
Maintenance Blinded Period	MPP	Lebrikizumab 250 mg Q4W_Res/ Lebrikizumab 250 mg Q4W; Lebrikizumab 250 mg Q2W_Res/ Lebrikizumab 250 mg Q4W; Lebrikizumab 250 mg Q2W_Res/ Lebrikizumab 250 mg Q2W; Total	LEB250Q4W_Res/ LEB250Q4W; LEB250Q2W_Res/ LEB250Q4W; LEB250Q2W_Res/ LEB250Q2W; Total	No Between-Group or Overall Comparisons
Maintenance Blinded Period	MSP	Placebo_Res/Placebo	PBO_Res/PBO	No Between-Group or Overall Comparisons
Maintenance Escape Period	Maintenance W16 Escape Population	Placebo_NonResp/Lebrikizumab 250 mg Q2W; Lebrikizumab 250 mg Q4W_NonResp/Lebrikizumab 250 mg Q2W; Lebrikizumab 250 mg Q2W_NonResp/Lebrikizumab 250 mg Q2W; Total	PBO_NonResp/ LEB250Q2W; LEB250Q4W_NonResp/ LEB250Q2W; LEB250Q2W_NonResp/ LEB250Q2W; Total	No Between-Group or Overall Comparisons

Maintenance Escape Period	Maintenance W20-64 Escape Population	Placebo/Placebo/Lebrikizumab 250 mg Q2W; Lebrikizumab 250 mg Q4W/ Lebrikizumab 250 mg Q4W/ Lebrikizumab 250 mg Q2W; Lebrikizumab 250 mg Q2W/ Lebrikizumab 250 mg Q4W/ Lebrikizumab 250 mg Q2W; Lebrikizumab 250 mg Q2W/ Lebrikizumab 250 mg Q2W/ Lebrikizumab 250 mg Q2W; Total	PBO/PBO/LEB250Q2W; LEB250Q4W/ LEB250Q4W/ LEB250Q2W; LEB250Q2W/ LEB250Q4W/ LEB250Q2W; LEB250Q2W/ LEB250Q2W/ LEB250Q2W;	No Between-Group or Overall Comparisons
Combined Induction and Maintenance Periods	All Lebrikizumab Safety Population	Any Lebrikizumab	N/A	No Between-Group or Overall Comparisons
Combined Induction and Maintenance Periods + FU	All Lebrikizumab Safety Population	Any Lebrikizumab	N/A	No Between-Group or Overall Comparisons

Abbreviations: FU = follow-up; ITT = intent-to-treat; LEB = lebrikizumab; NonResp = non-responder; PBO = placebo; PPS = per protocol set; Q2W = every 2 weeks; Q4W = every 4 weeks; Res = responder.

4. Statistical Analyses

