The SAP will be finalized prior to unblinding and it will include a more technical and detailed description of the statistical analyses described in this section. This section is a summary of the planned statistical analyses of the most important endpoints, including primary and key secondary endpoints.

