#### **9.4.1.2. Adjustment for Multiple Comparisons**

The prespecified graphical multiple testing approach (Bretz et al. 2011) will be implemented to control the overall type I error rate at a 2-sided alpha of 0.05 for superiority tests for the hypotheses for the co-primary and major secondary endpoints.

The major secondary endpoints are as follows:

- percentage change in EASI score from baseline to Week 16
- proportion of participants achieving EASI-90 ( $\geq 90\%$  reduction from baseline in EASI score) at Week 16, and
- proportion of participants with an Itch NRS of  $\geq 4$ -points at baseline who achieve a  $\geq 4$ -point reduction from baseline to Weeks 1, 2, 4 and 16.

The graphical approach is a closed testing procedure; hence, it strongly controls the family-wise error rate across all endpoints (Alosh et al. 2014). The Week 16 endpoints of IGA 0/1 and EASI-75 represent a primary endpoint family. The graphical testing scheme will sequentially test the co-primary endpoints for lebrikizumab 250 mg Q2W to placebo first before proceeding to test the co-primary endpoints for lebrikizumab 250 mg Q4W to placebo and the major secondary endpoints during the Induction Period. Details of the specific graphical testing scheme (including testing order, interrelationships, type I error allocation, and the associated propagation) will be prespecified in the SAP prior to first unblinded efficacy analysis.

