- serum chemistry
- hematology
- urinalysis laboratory testing
- physical examination
- pulse and blood pressure (vital signs)

- chest x-ray
- concomitant medications, and
- monitoring of hormone levels and growth parameters (adolescents only).

Serum samples will be collected for pharmacokinetics (PK) analysis and immunogenicity.

Participants who terminate the study early or complete the 68-week treatment period will receive a safety follow-up visit at which vital signs will be measured, C-SSRS self-harm supplement and self-harm follow-up form will be completed, and PK and immunogenicity samples will be collected.

Participants to use mid- and low-potency TCS or TCIs which will be used in treatment period ≥ 7 days prior to the Baseline visit (Day 1).

Low-potency TCS or TCIs may be used for sensitive areas only.

Participants who receive rescue treatment in the induction period will be eligible to continue to the Escape arm and receive 250 mg lebrikizumab Q2W.

At Week 16, site personnel will instruct the participant or their caregiver on the proper injection technique.

At Week 16 and Week 18, participants or their caregiver will administer study intervention under site personnel supervision.

2. Statistical Hypotheses

The following is a list of primary and major secondary endpoints to be tested. The subscript for **H** denotes study intervention arms in the comparisons (I2 = lebrikizumab 250 mg Q2W, I4 = lebrikizumab 250 mg Q4W and p = placebo), the numerical identifier of the endpoint within the comparison, and the type of hypothesis (0 for null, 1 for alternative), respectively.

Co-Primary Null Hypotheses:

- **H_{I2p,1,0}**: Proportion of lebrikizumab 250 mg Q2W participants achieving EASI-75 at Week 16 is equal to the proportion of placebo participants achieving EASI-75 at Week 16
- **H_{I2p,2,0}**: Proportion of lebrikizumab 250 mg Q2W participants achieving IGA score of 0 or 1 and a reduction of ≥ 2 -points from baseline to Week 16 is equal to the proportion of placebo participants achieving IGA score of 0 or 1 and a reduction of ≥ 2 -points from baseline to Week 16
- **H_{I4p,1,0}**: Proportion of lebrikizumab 250 mg Q4W participants achieving EASI-75 at Week 16 is equal to the proportion of placebo participants achieving EASI-75 at Week 16

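### SAP 2.1 lists Itch NRS response at Week 16 only among the key secondary tests, although Protocol 9.4.1.2 puts Weeks 1, 2 and 4 under alpha control as well, so the confirmatory status of early itch is contradictory.

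*SAP*

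**What the plan says.** Protocol 9.4.1.2 commits to control of the overall two-sided 0.05 level for "superiority tests for the hypotheses for the co-primary and major secondary endpoints". The list that follows in that section includes the itch responder endpoint, with "reduction from baseline to Weeks 1, 2, 4 and 16". The section leaves the details of the scheme to the SAP, "including testing order, interrelationships, type I error allocation, and the associated propagation".

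SAP 1.1 repeats the four itch weeks under major secondary. SAP Section 2 opens with "The following is a list of primary and major secondary endpoints to be tested" and sets out 12 major secondary null hypotheses, six per dose, among them Itch at Weeks 16, 4, 2 and 1.

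SAP 2.1 describes the family as the co-primary and key secondary endpoints. Its list, introduced by "The following is a list of co-primary and key secondary endpoints to be tested", gives the two co-primary endpoints for both doses and three key secondary endpoints for Q2W against placebo: EASI percentage change, EASI-90 and Itch NRS response, all at Week 16. It adds that "any hypothesis tests with a multiple testing adjusted p-value of less than 0.05 will be considered statistically significant".

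SAP 4.3.2 says that the primary and key secondary endpoints receive the multiplicity-controlled analysis of Section 2.1. SAP Appendix 2 labels the itch responder analysis key secondary at Weeks 1, 2, 4 and 16. SAP 4.9 lists two changes from the protocol: removal of the skin-pain-free-days endpoint and redefinition of the Maintenance populations. The SAP version history says only that the graphical scheme in Section 2.1 was updated, in order to prespecify it.

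**The concern.** Membership of the tested family decides which results can be reported as confirmatory. A reader who follows the protocol, or Appendix 2 together with SAP 4.3.2, would take a positive itch result at Week 1, 2 or 4 as multiplicity-controlled. A reader who follows the 2.1 list would take it as a nominal secondary finding. Onset of itch relief is a result that a sponsor may want to claim, and the plan should not leave its status to be settled after the data are seen.

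The protocol hands the SAP the order, the weights and the passing of alpha. It does not hand over which of its named endpoints are in the family. Dropping three of them is therefore a departure from the protocol, and the SAP does not record it as one.

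**Working it through.** **1. The plan's own figure.** The documents state power above 95% (Q2W) and above 80% (Q4W) for the co-primary endpoints. The inputs are in Protocol 9.2 and SAP 5: 120:80:80 participants; IGA 0/1 rates of 38%, 33% and 13%; EASI-75 rates of 58%, 53% and 20%; two-sided Fisher exact test at 0.05. Exact enumeration gives:

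| Comparison | IGA 0/1 | EASI-75 | Product |
|---|---|---|---|
| Q2W vs placebo (120:80) | 0.9795 | 0.9998 | 0.979 |
| Q4W vs placebo (80:80) | 0.8254 | 0.9906 | 0.818 |

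Both stated figures are reproduced. Nothing in this point changes them.

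**2. Counting hypotheses.** SAP Section 2 has 4 co-primary + 12 major secondary = 16. The SAP 2.1 list has 4 + 3 = 7. The difference is 9: three Q2W early-itch tests and six Q4W secondary tests.

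**3. Where the three Q2W early-itch tests stand, place by place.**

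| Place | Itch weeks | Status given |
|---|---|---|
| Protocol 9.4.1.2 | 1, 2, 4, 16 | major secondary, alpha-controlled |
| SAP 1.1 | 1, 2, 4, 16 | major secondary |
| SAP 2 | 16, 4, 2, 1 | major secondary, to be tested |
| SAP 2.1 list | 16 | key secondary, in the graph |
| SAP Appendix 2 | 1, 2, 4, 16 | key secondary |
| SAP 4.9 | none | no change recorded |

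**4. Could key be a deliberate subset of major?** Neither document defines it so. Protocol 9.4.1 describes its statistical section as covering "the most important endpoints, including primary and key secondary endpoints", and the multiplicity text in the same section then speaks of major secondary endpoints. The SAP's own Appendix 2 calls early itch key secondary. Taken with SAP 4.3.2, that requires control of early itch, and the 2.1 list does not provide it.

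**5. The unseen graph.** There are two cases. If it holds only the listed tests, the protocol's control of early itch is not delivered. If it also holds early itch, the 2.1 list is incomplete. SAP text needs correction in both.

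**6. The nominal rate, for scale only.** Suppose the three early-itch tests were read at an unadjusted two-sided 0.05 with all nulls true. With independence, the chance of at least one p<0.05 is 1 - 0.95^3 = 0.143. The documents give no correlation between weeks. For equicorrelated normal statistics with assumed correlations of 0, 0.3, 0.5, 0.7 and 0.9, numerical integration gives 14.3%, 13.6%, 12.5%, 10.9% and 8.4%.

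**7. Tipping-point weeks.** SAP 4.1.6.1.2 names Itch at Week 16 only, and its seed table has one itch seed, for Week 16. Appendix 2 schedules the itch tipping-point analysis at Weeks 1, 2, 4 and 16. This conflict does not depend on the graph.

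**The case against.** The strongest reply is that the SAP body is more consistent than the table suggests. Section 2.1 itemises key secondaries at Week 16, and the tipping-point section agrees for itch, so the Appendix 2 label may simply be an error. This has force for the conflict inside the SAP. It does not remove the departure from Protocol 9.4.1.2, which names the early weeks.

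On recording, Protocol 9.4.1 asks for changes in the SAP and the study report without naming Section 4.9, and the version history does mention an update to the scheme. But that entry does not say that endpoints named in the protocol were left out, and it gives no reason for leaving them out.

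A reader might infer from the figures in step 6 that the trial's 5% family-wise error is exceeded. The documents do not support that. A test outside the graph has no adjusted p-value, so on the 2.1 rule it yields no controlled claim, and error control over the listed tests stands. The figures are nominal flag rates, as for any uncontrolled secondary endpoints. Nor does 2.1 say that only adjusted results may be called significant: SAP 4.7.2.1 uses the term for an interaction test at the 10% level.

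A reader might also infer that the six Q4W secondaries have been dropped against the protocol. That goes too far. The protocol does not expressly place them in the graph. Section 2.1 names both doses for the co-primaries and Q2W alone for the key secondaries, which looks deliberate. Appendix 2 lists both dose comparisons on nearly every inferential row, so its label there says little about dose. What remains is a lack of clarity between SAP 2, 2.1 and Appendix 2.

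**Conclusion.** The point holds for the three Q2W early-itch tests: the protocol puts them in the controlled family, the SAP 2.1 list leaves them out, and other parts of the SAP point both ways. This should be fixed, and it is a textual contradiction that needs no assumption to establish. Whether the remedy is a list correction or a change to the scheme depends on the graph. The mismatch in Itch tipping-point weeks is certain but minor, and the unclear status of the Q4W secondaries is a lesser matter of labelling. Co-primary inference, its power, and error control for the listed tests are unaffected.

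**What to change.** Before first unblinding, make SAP 2, SAP 2.1, the graph and Appendix 2 name one family.

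- If the graph already holds early itch, correct the 2.1 list.
- If it does not, choose one of two routes. (a) Add Q2W Itch at Weeks 4, 2 and 1, the order in which SAP 2 numbers them, as terminal nodes that receive alpha only after the listed tests are rejected. (b) Relabel them other secondary with nominal p-values, record the departure from Protocol 9.4.1.2 and its justification in SAP 4.9, and decide under the Protocol 9.4.1 rule on principal features whether an amendment is needed.
- Make the Appendix 2 key secondary labels match 2.1 by dose.
- Give the same Itch weeks in the text and seed table of SAP 4.1.6.1.2 and in Appendix 2.

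The cost is mostly rewording. Route (a) takes no power from the listed tests, but the added tests open only if all of those succeed. The Q4W IGA test alone has Fisher power 0.825 at full alpha under the planning rates, so the added tests would stay closed in at least 1 - 0.825 = 0.175 of trials. That bound uses the planning test rather than the planned CMH test. Under route (b) early itch loses confirmatory status.

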4.1. General Considerations

Statistical analysis of this study will be the responsibility of Eli Lilly Japan K.K. (Lilly). The latest version of the Medical Dictionary for Regulatory Activities (MedDRA) will be used.

Analyses and summaries from assessment of endpoints described in the protocol are planned to be included in a clinical study report (CSR). Analyses and summaries for key safety data are also planned to be included in the CSR. Results from additional efficacy analysis and other safety analyses may also be provided in the CSR as deemed appropriate.

Not all displays described in the SAP will necessarily be included in the CSRs. Any display described and not provided in the CSR would be available upon request. Not all displays will necessarily be created as a “static” display. Some may be incorporated into interactive display tools instead of or in addition to a static display. Any display created interactively will be included in the CSR if deemed relevant to the discussion.

All statistical processing will be performed using SAS® unless otherwise stated. Except where noted, all statistical tests will be two-sided and will be performed at the 0.05 level of significance.

The Schedule of Visits and Procedures outlined in the protocol specifies the allowable windows for assessments. Assessments performed outside these windows will not be excluded from any analysis, unless specified otherwise.

Any change to the data analysis methods described in the protocol will require a protocol amendment ONLY if it changes a principal feature of the protocol. Any other change to the data analysis methods described in the protocol and the justification for making the change will be described in the CSR.

4.1.1. General Considerations for Analyses During Induction Period

Induction Period starts after the first injection of study intervention at Baseline Visit (Visit 2, Week 0) and ends prior to the first injection of study intervention at Week 16 or the early termination visit (ETV) (between Week 0 and Week 16). For participants who were randomized but discontinued the study before the first injection, the Induction Period starts on the date of randomization. For participants who were randomized but received the first injection after the date of randomization, the Induction Period starts on the date of first injection.

Baseline will be defined as the last available value before the first injection for efficacy and health outcome analyses. In most cases, this will be the measure recorded at Baseline Visit (Week 0). If the participant does not take any injection, the last available value on or prior to randomization date will be used. Change from baseline will be calculated as the visit value of interest minus the baseline value.

For Itch Numeric Rating Scale (NRS), Skin Pain NRS and Sleep-Loss due to Itch collected via electronic Clinical Outcome Assessment (eCOA), the baseline period is the 7-day window prior to the first injection. A participant must have responses on at least 4 of 7 days to calculate a

baseline weekly mean. If a participant has responses for 3 or less days, the baseline mean value will be considered missing. eCOA data for Itch NRS, Skin Pain NRS and Sleep-loss due to Itch are mapped to study visit per [Appendix 12](#).

For the safety analyses, the following baselines will be used. For safety analyses using a baseline period, the baseline period is defined as the time from Screening Visit (Visit 1) to the date/time of the first injection in the Induction Period.

- Treatment-emergent adverse events (TEAEs): baseline will be all results (including medical histories which are ongoing at the date of informed consent) recorded during the baseline period.
- Treatment-emergent abnormal laboratory and vital signs results: baseline will be all results recorded during the baseline period.
- Change from baseline to last post-baseline observation or to each scheduled post-baseline visit for laboratory and vital signs results: baseline will be the last scheduled non-missing assessment recorded during the baseline period.

The randomization to treatment groups is stratified by age (adolescent participants 12 to <18 years versus adults ≥ 18 years) and baseline disease severity (IGA 3 versus 4). Unless otherwise specified, the statistical analysis models for the Induction Period will adjust for age and baseline disease severity.

For assessments of the primary endpoints and other binary efficacy and health outcome endpoints, the following will be provided:

- Crude proportions for each treatment group along with the 95% two-sided asymptotic (that is, not continuity corrected) confidence intervals (CIs).
- The estimated common risk difference along with 95% CIs: The common risk difference is the difference in proportions adjusted for the stratification factors. SAS® PROC FREQ will be used for the estimates and CIs, where the CIs are calculated by using Mantel-Haenszel-Sato method (Sato 1989).
- Cochran-Mantel-Haenszel (CMH) test will be used to compare the treatment groups while adjusting for the stratification factors. The CMH p-value will be reported, and the CMH adjusted odds ratio (OR) along with the 95% two-sided asymptotic (that is, not continuity corrected) CIs.

Treatment comparisons of key continuous efficacy variables and health outcome variables at each post-baseline time point will be made using analysis of covariance (ANCOVA) with the following in the model: treatment group, baseline value, and stratification factors. Type III tests for least squares (LS) means will be used for statistical comparison between treatment groups. The LS mean difference, standard error (SE), p-value, and 95% CI, unless otherwise specified, will also be reported.

Treatment comparisons of other continuous efficacy variables and health outcome variables with multiple post-baseline measurements will be made using mixed-model for repeated measures (MMRM). When MMRM is used, the model includes treatment, baseline value, visit, the interaction of the baseline value-by-visit, the interaction of treatment-by-visit, and the stratification factors as fixed effects. The covariance structure to model the within-participant

errors will be unstructured. If this analysis fails to converge, the heterogeneous autoregressive [ARH(1)], followed by the heterogeneous compound symmetry (CSH), followed by the heterogeneous Toeplitz (TOEPH), followed by the autoregressive [AR(1)], followed by the compound symmetry (CS) will be used. The restricted maximum likelihood (REML) will be used. The Kenward-Roger method will be used to estimate the denominator degrees of freedom. Type III tests for the LS means will be used for the statistical comparison; the 95% CI will also be reported.

For variables that are not collected at each post-baseline visit, data may exist at visits where the variable was not scheduled to be collected. In these situations, data from the early discontinuation visit that do not correspond to the planned collection schedule will be excluded from the MMRM analysis (Andersen and Millen 2013). Also for by-visit summaries/displays such as boxplots, the weeks when data was not scheduled to be collected may not be displayed. However, unscheduled assessments within any defined study period will still be used in the shift analyses, and for imputing values for the change from baseline to last observation carried forward (LOCF) endpoint analyses.

The Kaplan-Meier product limit method may be used to estimate the survival for time to event analyses. The log-rank test stratified by the stratification factors will be reported. A Kaplan-Meier plot of the time to event by treatment group may be provided.

Unless specified otherwise, Fisher's exact test will be used for AEs and other categorical safety measures. ORs will be created with lebrikizumab treatment as the numerator, and placebo as the denominator. Continuous vital signs and laboratory values will be analyzed by an ANCOVA with treatment and baseline value in the model.

